10.5.2 Safety

For all safety analyses, the safety set will be used, unless otherwise specified. The assessment of safety will be based mainly on the frequency of adverse events and on the number of laboratory values that fall outside of pre-determined ranges. All individual safety data reported in the clinical data base will be listed by patient and dose level.

The overall observation period will be divided into three mutually exclusive segments:

- pre-treatment period: from day of patient's informed consent signature to the day before first dose of study treatment.
- on-treatment period: from day of first dose of study treatment to 30 days after last dose of study medication.
- post-treatment period: starting at day 31 after last dose of study treatment.

10.5.2.1 Adverse events

The incidence of treatment-emergent adverse events (new or worsening from baseline) will be summarized by primary system organ class, severity based on the National Cancer Institute's Common Terminology Criteria for Adverse Events (CTCAE) version 4.03, type of adverse event, and relationship to the study drug by dose level on the pool of patients recruited during the dose escalation part of the study as well as on the complete pool of patients (including dose escalation and Phase II parts). Deaths reportable as SAEs and non-fatal serious adverse events will be listed by patient and tabulated by primary system organ class, type of adverse event, and dose level.

DLTs will be listed and their incidence summarized by primary system organ class, worst grade based on the CTCAE version 4.03, type of adverse event, and by dose level in the dose escalation part. The dose-determining set will be used for these summaries.

Details of analysis to be performed are given in the Reporting and Analysis Plan (RAP).

10.5.2.2 Laboratory abnormalities

All laboratory values will be converted into SI units and the severity grade calculated using CTCAE, version 4.03. Parameters for which a grading does not exist will be classified into low/normal/high group by means of laboratory normal ranges.

For each laboratory test (e.g. hematology, biochemistry etc) a listing of laboratory values will be provided by laboratory parameter, patient, and dose level. The frequency of notable laboratory abnormalities (i.e., newly occurring CTC grade 3 or 4 laboratory toxicities) will be displayed by parameter, cycle and dose level. Similarly, the frequency of all laboratory abnormalities will be displayed by parameter, worst CTCAE grade experienced and dose level. A separate listing will display notable laboratory abnormalities.

Laboratory data will be summarized by presenting grade shift tables for those parameters for which CTCAE allows classification. All remaining data will be summarized by presenting shift tables based on normal ranges.

Laboratory data will be also be displayed by presenting summary statistics of raw data and change from baseline values (means, medians, standard deviations, ranges).

10.5.2.3 Other Safety data

Any other safety information collected will be listed and notable values will be flagged. Any statistical tests performed to explore the data will be used only to highlight any interesting comparisons that may warrant further consideration. Additionally, the following outputs will be produced:

ECG

- shift table baseline to worst on-treatment result for overall assessments
- listing of ECG evaluations for all patients with at least one abnormality.

Vital signs

- shift table baseline to worst on-treatment result
- table with descriptive statistics at baseline, one or several post-baseline time points and change from baseline to this/these post-baseline time points.

Ocular

- Listing of ocular assessment for all patients with at least one abnormality will be presented.

10.5.2.4 Tolerability

Tolerability of study drug treatment will be assessed by summarizing the number of treatment dose interruptions and dose reductions. Reasons for dose interruption and dose reductions will be listed by patient and summarized. Cumulative dose, dose intensity and relative dose intensity of MEK162, LGX818 and LEE011 will be listed by patient and summarized. Categories for relative dose intensity of the combination MEK162, LGX818 and LEE011 will be specified as < 0.5 , $\geq 0.5 - < 0.75$, $\geq 0.75 - < 0.9$, $\geq 0.9 - < 1.1$ and ≥ 1.1 . The number and proportion of patients within each category will be presented.

10.5.3 Pharmacokinetics

A secondary objective of this study is to determine the single and multiple dose pharmacokinetic profile of the dual combination (MEK162 and LGX818), and the triple combination (LGX818 and MEK162 and LEE011).

For plasma LGX818, the LLOQ is 1.0 ng/mL, for MEK162 is 5.0 ng/mL and LEE011 is 1.0 ng/mL. All concentrations below the LLOQ or missing data will be labeled as such in the concentration data listings. Concentrations below the LLOQ will be treated as zero in summary statistics. The parameters displayed on [Table 10-1](#) will be estimated and reported.

Descriptive graphical plots of individual and mean plasma concentration (per treatment) along with its time course will be generated. Further graphical exploratory analyses will be carried out if deemed appropriate. Pharmacokinetic parameters for each dose cohort will be analyzed by descriptive statistics, including the mean, SD, CV% or median (range). Since t_{\max} is generally evaluated by a non-parametric method, median values and ranges will be given for this parameter.

Assessment of dose-proportionality, inter- and intra-individual variability and steady-state attainment will be conducted. If appropriate, an analysis of variance (ANOVA) will be performed on log-transformed AUCs and C_{max} using a linear mixed effect model to assess day effect.

Details of PK analysis presented will be given in the Reporting and Analysis Plan. Any other exploratory analysis will be conducted if necessary.

Table 10-1 PK parameters

Variable	Definition
C_{max}	Maximum observed plasma concentration after drug administration [mass x volume ⁻¹]
$C_{max,ss}$	Maximum observed plasma concentration during a dosing interval at steady state [mass x volume ⁻¹]
C_{trough}	Measured concentration at the end of a dosing interval at steady state (taken directly before next administration) [mass x volume ⁻¹]
t_{max}	Time to reach C_{max} [time]
$t_{max,ss}$	Time to reach C_{max} at steady state [time]
AUC_{tau}	Area under the concentration-time curve during a dosing interval [mass x time x volume ⁻¹]
AUC_{inf}	Area under the concentration-time curve from time zero to infinity with extrapolation of the terminal phase [mass x time x volume ⁻¹]
$AUC_{tau,ss}$	Area under the concentration-time curve during a dosing interval at steady state [mass x time x volume ⁻¹]
$t_{1/2}$	Elimination half-life associated with the terminal slope (λ_z) of a semi logarithmic concentration-time curve [time]
CL/F	Apparent total plasma clearance of drug after oral administration [volume x time ⁻¹]
V/F	Apparent volume of distribution [volume]
R_A	Accumulation ratio calculated as $AUC_{tau,ss}/AUC_{tau,dose1}$

In addition, in case drug accumulation is observed upon multiple dosing, additional PK parameters describing drug accumulation will be added to the analysis (i.e. effective half-life).

10.5.3.1 Data handling principles

10.5.3.1.1 Analysis sets

Only PK blood samples with date and time and for which the last prior dose dates and times are adequately recorded will be included in the PK analyses. Samples taken from patients who vomited within 4 hrs of dosing will be excluded from the analysis. The FAS will be used.

10.5.3.1.2 Basic tables, figures and listings

Descriptive statistics (mean, standard deviation, CV% or median (range)) will be presented for all parameters for each dose cohort. When a geometric mean is presented, it will be stated as such. CL/F will be assessed for MEK162, LGX818 and LEE011, as applicable, and only median values and ranges will be given for t_{max} .

Descriptive graphical plots of individual plasma concentration by time will be generated, as will mean concentration time profiles for MEK162, LGX818 and LEE011, as applicable. Further graphical exploratory analyses will be carried out if deemed appropriate.

10.5.3.1.3 Advanced data analysis methods

CCI

The text 'CCI' is followed by three large black redaction boxes covering the majority of the page content under this section.

10.5.4 Biomarkers

10.5.4.1 Outline of the data analysis

As a project standard, only patient pre-selection and PD markers collected in the clinical database will be analyzed by the Sponsor. Since this clinical trial was not designed to address specific hypotheses related to patient pre-selection or PD markers, the analysis of this data should be viewed as exploratory and hypotheses generating. Analytical results from such analyses may be used to generate additional hypotheses that must then be verified with data derived from subsequent clinical trials. No adjustment for multiple comparisons is planned.

If the number of samples is inadequate to perform a rigorous data analysis, then the available data will only be listed. Additional analyses that may be performed after the completion of the end-of-study clinical study report will be documented in separate reports. These analyses may include but are not limited to the meta-analysis of data from this study combined with data from other studies or the analysis of patient pre-selection or PD markers generated from samples collected during the study but analyzed after the database lock and completion of the clinical study report. The data analysis will be described in an addendum of the RAP or in a stand-alone analysis plan document, as appropriate.

10.5.4.2 Data handling principles

All measurements below their respective LLOQs or missing data will be labeled as such in the concentration data listings. Measurements below the LLOQ will be treated as zero in summary statistics. Change from baseline analyses will only be performed on patients with measurable samples and pre- and post-treatment time points.

10.5.4.3 Data analysis principles

10.5.4.3.1 Analysis sets

The FAS will be used for all analyses. The number of patients with measurable samples will be identified in the summaries and relevant proportions will be calculated against this number of patients.

10.5.4.3.2 Basic tables, figures and listings

To characterize baseline molecular status of molecules relevant to RAF/MEK/ERK and EGFR/PI3K/AKT signaling in tumor tissue in the Phase II parts of the study, baseline molecular status (mutation/amplification/expression) in tumor tissue of potential predictive markers (BRAF, HRAS, KRAS, NRAS, PTEN, cKIT, PIK3CA, MAP2K1, MAP2K2, ARAF, c-MET, RAFI, EGFR) will be summarized by patient group. All biomarker assessments obtained from the full complement of fresh pre- and post-treatment paired tumor/skin biopsies collected in the trial will be listed by patient and time point and summarized using descriptive statistics by time point.

All biomarker assessments only collected at baseline will be listed by patient and summarized using descriptive statistics.

All biomarker assessments obtained from tumor samples from patients with disease progression will be listed by biomarker and by patient.

10.5.4.3.3 Advanced analysis methods

CCI

10.5.5 Resource utilization

Not applicable.

10.5.6 Patient-reported outcomes

Not applicable.

CCI

10.7 Interim analysis

An interim analysis for futility will be performed in the phase II BRAF V600 mutant mCRC arm (dual-combination arm 1), when 14 patients (50% of the total sample size) have completed 4 cycles of treatment. As mentioned in Section 10.8, study results are successful if 9 responses are observed at the end of the trial. At the interim analysis, if the predictive probability of success is < 13%, i.e. if less than 3 responses (DCR at week 16) are observed, this study arm will be stopped for futility.

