The primary purpose of the proposed dose-finding Phase Ib study is to estimate the MTD(s) and/or the recommended Phase II dose(s) (RP2D(s)) of the dual (LGX818 and MEK162) and triple (LGX818 and MEK162 and LEE011) combinations in patients with locally advanced or metastatic melanoma, mCRC or any other solid tumor upon agreement with the Sponsor, positive for either V600E BRAF mutation, or any other BRAF mutation at the V600 codon (e.g. V600K/D/R).

Once the MTD/RP2D has been determined for the dual combination, additional patients will be enrolled in three Phase II arms to further assess the clinical anti-tumor efficacy of the combination. The Phase II arm 1 will assess the disease control rate (DCR) of the LGX818 and MEK162 combination in patients with BRAF V600 mutant metastatic CRC. In the Phase II arm 2, the study will assess the objective response rate (ORR) of the combination in metastatic BRAF mutant melanoma patients who have progressed after prior treatment with a selective BRAF inhibitor (e.g. PLX4032, GSK2118436). In the Phase II arm 3, the study will assess the objective response rate (ORR) of the combination in metastatic BRAF mutant melanoma patients who are naïve to prior treatment with a selective BRAF inhibitor. The DCR (defined as patients with CR or PR or SD) rather than the ORR (defined as patients with CR or PR) will be used to evaluate clinical benefit in Phase II arm 1, as only a limited number of patients with BRAF mutant mCRC have experienced tumor shrinkage in clinical studies with RAF or MEK inhibitors (see [Section 1.1.3](#)), with more patients achieving stable disease (SD) than response. Also an interim analysis for futility will be performed in arm 1 after 50% of the total number of patients in this arm have completed four cycles of treatment, to allow stopping early for futility when there is no treatment effect. All three Phase II arms will further assess the safety of the LGX818 and MEK162 combination.

For the triple combination, once the MTD/RP2D has been determined additional metastatic BRAF mutant melanoma patients who are naïve to prior treatment with a selective BRAF inhibitor will be enrolled in arm A to assess the ORR of this triple combination. The safety of the triple combination will also be assessed in the Phase II population.

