4.2 Timing of interim analyses and design adaptations

An interim analysis for futility will be performed during the Phase II part of the study in arm 1 dual combination (BRAF mutant mCRC patients) after 50% of the total number of patients in this arm have completed four cycles of treatment, to allow stopping early for futility when there is no treatment effect (see also [Section 4.1-Phase II](#) and [Section 10.7](#)).

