10.8 Sample size calculation

Phase Ib

Dose escalation: Cohorts of 3 to 6 evaluable patients will be enrolled in the dose escalation part including at least six patients at the MTD/RP2D level, as described in [Section 6.2.4](#).

Multiple cohorts may be sequentially enrolled to the same dose level. Additional cohorts of 1 to 6 patients may be enrolled at any dose level below the estimated MTD/RP2D for further elaboration of safety and PK parameters as required. At least 18 patients are expected to be treated in the dual-combination dose-escalation part of the study, for the model to have reasonable operating characteristics relating to its MTD recommendation (see [Appendix 5](#) for details). At least 12 patients are expected to be treated in the triple-combination dose-escalation part of the study.

Phase II

Arm 1 dual combination: Based on the prior distribution and decision rules described in [Section 10.4](#), it was explored how likely it is to wrongly declare activity given the true DCR = 20%, and how likely it is to correctly declare activity given the true DCR = 40%, when 28 patients are evaluated.

- If the true DCR = 20%, the probability to wrongly declare activity (i.e. seeing at least 9 patients with SD or better) is 9.0%.
- If the true DCR = 40%, the probability to correctly declare activity (i.e. seeing at least 9 patients with SD or better) is 85.2%.

If 9 out of 28 patients have at least SD or better, then the posterior risk of the true DCR being in the unacceptable category is 7.0%.

Note: if the interim analysis is performed, the probability to correctly declare activity if the true DCR = 40% is 82.3%.

Arm 2 dual combination: Based on the prior distribution and decision rules described in [Section 10.4](#), it was explored how likely it is to wrongly declare activity given the true ORR = 10%, and how likely it is to correctly declare activity given the true ORR = 20%, when 41 patients are evaluated:

- If the true ORR = 10%, the probability to wrongly declare activity (i.e. seeing at least 7 responses) is 11.0%.
- If the true ORR = 20%, the probability to correctly declare activity (i.e. seeing at least 7 responses) is 73.9%.

If 7 out of 41 patients have PR or CR, then the posterior risk of the true ORR being in the unacceptable category is 9.8%.

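### Arm 1 futility look: the trigger counts only patients who completed four cycles, so the interim set is enriched for disease control and the look comes late or not at all when the regimen is inactive

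*Protocol*

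**What the plan says.** Section 10.7 places the arm 1 look "when 14 patients (50% of the total sample size) have completed 4 cycles of treatment". Section 4.2 says it is done "after 50% of the total number of patients in this arm have completed four cycles of treatment, to allow stopping early for futility", and sections 2.1 and 4.1 carry the same condition.

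The arm is stopped "if the predictive probability of success is < 13%, i.e. if less than 3 responses (DCR at week 16) are observed". At the end, "study results are successful if 9 responses are observed at the end of the trial". Section 10.8 gives the operating characteristics for the case "when 28 patients are evaluated".

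Other provisions that matter here:

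- Cycles last 28 days (6.2.1), and the arm 1 primary variable is DCR at week 16 (10.4.1).
- Treatment runs until progression, unacceptable toxicity or withdrawal of consent (4.1). It continues beyond progression only in special circumstances (6.1.5).
- Phase II on-treatment scans fall at the end of Cycle 2 and every 8 weeks after that (7.2.1).
- Phase II patients are not replaced (7.1.4.2).

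**The concern.** The milestone and the endpoint share a time point, and both depend on not having progressed. A patient whose week-8 scan shows progression normally stops then, never completes four cycles and, as the trigger is worded, never enters the interim set. Membership of the 14 therefore depends on the outcome being tested.

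This has two effects when the regimen is inactive. Completers accumulate slowly, so the look is late or never reached within 28 patients. If it is reached, the 14 contain a higher share of controlled patients than the arm as a whole, so fewer than 3 is less likely to be seen. Stopping early when there is no treatment effect is the only stated purpose of the look, and that is what is weakened.

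**Working it through.** **Inputs from the protocol.** n = 28; success at 9 or more; interim at 14; stop at 2 or fewer; prior Beta(0.428, 1); DCR 20% as unacceptable and 40% as the target (10.4.2.2, 10.7, 10.8).

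**Step 1: reproduce the plan's figures on unselected patients.**

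- P(X ≥ 9 | 28, 0.2) = 9.00% (stated 9.0%).
- P(X ≥ 9 | 28, 0.4) = 85.15% (stated 85.2%).
- Posterior P(DCR < 0.20 | 9 of 28), from Beta(9.428, 20) = 7.00% (stated 7.0%).
- Predictive probability of at least 9 of 28 given x of 14, beta-binomial with Beta(0.428 + x, 15 − x) for the remaining 14: 2.5% at x = 2 and 13.4% at x = 3. This agrees with the stated rule of below 13%, meaning fewer than 3.
- Success probability with the look at DCR 40% is 84.1%, against 82.3% stated. This is within 2 points but not exact, and nothing below depends on it.

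The rule was therefore evidently worked out for 14 patients taken without regard to outcome.

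**Step 2: performance on 14 unselected patients.** P(X ≤ 2 | 14, d) is 84.2% at d = 10%, 44.8% at 20%, 16.1% at 30% and 4.0% at 40%.

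**Step 3: performance under the literal trigger.** Let c be the probability of completing four cycles and d the week-16 DCR, and assume that every controlled patient is a completer. Then:

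- P(trigger) = P(Bin(28, c) ≥ 14)
- P(stop | trigger) = P(Bin(14, d/c) ≤ 2)

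The protocol gives no value for c, so a range is shown.

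| c | P(trigger) | d = 20%: P(stop given trigger) | d = 20%: both | d = 10%: P(stop given trigger) | d = 10%: both |
|---|---|---|---|---|---|
| 40% | 18.7% | 0.6% | 0.1% | 28.1% | 5.3% |
| 50% | 57.5% | 4.0% | 2.3% | 44.8% | 25.8% |
| 60% | 89.8% | 10.5% | 9.5% | 57.9% | 52.0% |
| 80% | >99.9% | 28.1% | 28.1% | 74.9% | 74.9% |
| Unselected 14 | – | – | 44.8% | – | 84.2% |

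**Step 4: timing.** Reaching 14 completers needs about 14/c patients: 35 at c = 40% and 28 at c = 50%, with 28 planned. The only figure in the protocol that bears on c is a median PFS of 3.7 months, about 16 weeks, for a different BRAF inhibitor in this disease (1.1.3). That would put c near 50% for a drug with some activity. At that rate the look falls, on average, when enrolment is complete.

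**Step 5: false-positive rate.** At DCR 20%, success probability is 9.0% without the look and 8.7% with it on 14 unselected patients. Missing the look cannot push it above 9.0%.

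**The case against.** A reader might infer that completing four cycles is the same as being controlled at week 16, so that the look cannot stop the arm. On that identity, P(at least 14 of 28 complete) is 0.04% at DCR 20%, and fewer than 3 controlled among 14 completers is impossible. The documents do not support the identity. The week-16 scan falls at the end of Cycle 4, so progression can be found in a patient who has just completed it, and treatment beyond progression is allowed in special circumstances. As an illustration, assume a constant hazard and stopping only at scan-detected progression. Then c = √0.20 = 44.7% at DCR 20%, and P(trigger) is about 35%. The 0.04% is an extreme. Even so, P(trigger and stop) in that illustration is 35.3% × 1.8% = 0.6%, far below 44.8%.

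It can also be said that the intent was plainly 14 unselected patients. Section 10.7 describes the 14 as half the sample size, the cut-off reproduces on that basis, and the full analysis set is the default (10.1.1) and is named for this DCR (10.4.1). Section 10.4.2.2 also classes patients who withdrew for progression or died of disease, without a post-dose scan, as failures. This is good evidence of intent, but none of it defines who makes up the 14. The failure rules classify patients already in an analysis, and the one in 10.4.3 is tied to the primary analysis. Elsewhere the protocol does add the missing alternative: evaluability for dose escalation is completion of a cycle or a DLT (6.2.4.2, 10.1.3). Nor is this a detail left to the analysis plan, because the protocol fixes the trigger itself in four places.

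Finally, enrolment is closed (14.10.1), so this text cannot now lead to further patients being enrolled. That stands, and it limits the practical consequence to reporting.

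**Conclusion.** The point holds as a defect in the definition of the interim set. The decision rule is sound for 14 unselected patients, but the trigger describes a set selected on an outcome tied to the endpoint. Over assumed completion rates of 40% to 80%, the chance of triggering and stopping is 0.1%–28.1% at DCR 20% against 44.8% for the rule on unselected patients. At DCR 10% it is 5.3%–74.9% against 84.2%. These figures rest on the assumed c, on all controlled patients being completers, and on DCR read as status at week 16.

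The loss is confined to early stopping in one 28-patient arm. Neither a raised false-positive rate nor a look that can never stop the arm follows from the documents. With enrolment closed, this is a correction of wording and a reporting requirement. It does not threaten the primary inference.

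**What to change.** In sections 2.1, 4.1, 4.2 and 10.7, define the interim set as the first 14 treated arm 1 patients. Take the look once each of them has had the week-16 assessment or has progressed, died or discontinued before it. Keep all 14 in the denominator and count those without documented week-16 disease control as failures. The cut-off of fewer than 3, the predictive-probability threshold and the sample size stay as they are.

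The cost is wording only, and the look comes no later than under the present text. Because enrolment is closed, the study report should state which 14 patients the interim actually used and how patients who stopped before week 16 were counted.
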